
 myositis/polymyositis, infusion-related reactions, pancreatitis, encephalitis. 
Potential risks for durvalumab include:
 
 other rare or less frequent events with a potential immune-mediated etiology, e.g., pericarditis, sarcoidosis, uveitis, and other events involving the eye (e.g., keratitis and optic neuritis), skin (e.g., scleroderma, vitiligo, and pemphigoid), and hematological (e.g., hemolytic anemia and immune thrombocytopenic purpura), rheumatological events (polymyalgia rheumatic and autoimmune arthritis), neuropathy/neuromuscular toxicities (e.g., myasthenia gravis, Guillain-Barre syndrome), vasculitis, and non-infectious meningitis. hypersensitivity reactions, including: 
 anaphylaxis and allergic reaction cytokine release syndrome immune complex disease infections (excluding urinary tract infection, bronchitis, sepsis, bacterial sepsis, and urosepsis) 		
Standard of Care		
NA	
Cisplatin: Cumulative renal toxicity associated with Cisplatin injection is severe. Other major dose-related toxicities are myelosuppression, nausea, and vomiting and other toxicities (vascular, serum electrolyte disturbance, hyperuricemia, neurotoxicity, ocular, and hepatotoxicity). Anaphylactic-like reactions to cisplatin injection have been reported.
	
Toxicity management of cisplatin, carboplatin, and etoposide will be according to the local labels.

Table 6 Risk Assessment

Identified and potential risk of clinical significance	Summary of data/rationale for risk	Mitigation strategy
	
Carboplatin: Bone marrow suppression is dose related and may be severe, resulting in infection and/or bleeding. Anemia may be cumulative and may require transfusion support. Nausea/vomiting is frequently observed as well as urea elevations and electrolyte disturbance. Anaphylactic-like reactions to carboplatin have been reported and may occur within minutes of carboplatin administration.
 
Etoposide: Dose-limiting bone marrow suppression is the most significant toxicity associated with etoposide therapy. Other possible adverse events are the occurrence of an anaphylactic reaction (chills, fever, tachycardia, bronchospasm, dyspnea, and hypotension), nausea/vomiting, asthenia/malaise, alopecia, chills, and/or fever.
	
Study procedures		

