8.2.3 Electrocardiograms

An electrocardiogram (ECG) will be performed at time points as specified in the SoA. Electrocardiograms should be obtained after the participant has been in a supine position for 5 minutes and recorded while the participant remains in that position. Resting 12-lead ECGs will be recorded at screening and as clinically indicated throughout the study (see Section 1.3). All participants will have triplicate 12-lead ECGs (about 5 minutes apart). The ECG needs to be performed prior to the onset of the IV therapy (AZD2811 + durvalumab) and approximately 15 minutes after the end of all IV therapies.

During Induction, if there are clinically relevant cardiac observations during an infusion, triplicate 12-lead ECGs (about 5 minutes apart), pre- and post-durvalumab infusion

(approximately 15 minutes of the end of infusion) should be performed at all subsequent infusions.

During Maintenance, if there are clinically relevant cardiac observations during an infusion, triplicate 12-lead ECGs (about 5 minutes apart) pre- and post-AZD2811 and pre- and post-durvalumab infusion (approximately 15 minutes of the end of infusion) should be performed at all subsequent infusions.

In case of clinically significant ECG abnormalities, including a Fridericia's Correction Formula (QTcF) value > 470 ms, 2 additional 12-lead ECGs should be obtained over a brief period, at 15 and 30 minutes, to confirm the finding. Sites may also report Bazett's Correction Formula (QTcB) if that is the local standard.

Situations in which ECG results should be reported as AEs are described in Section 8.3.5.

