9.4.1 General Considerations

The main aims of the study are to assess the efficacy, safety, and tolerability of the study intervention in participants who entered the maintenance phase with ES-SCLC.

All analyses will be descriptive, including summaries from Kaplan-Meier curves. Continuous variables will be summarized by the number of observations, mean, standard deviation, median, upper and lower quartiles (as applicable), minimum, and maximum. Log-transformed

data will include geometric mean, geometric standard deviation, and coefficient of variation (CV). Categorical variables will be summarized by frequency counts and percentages for each category. Unless otherwise stated, percentages will be calculated out of the population total for the relevant analysis.

The summaries, where applicable, will be presented by the following: All participants, participants who only entered the induction phase, and participants who entered the induction and maintenance phase, unless otherwise specified.

From CSP v8.0 onwards, the starting dose of AZD2811 in the maintenance phase was intended to be ~~CC1~~ [REDACTED], and the study would therefore report efficacy and safety by maintenance phase starting dose of AZD2811 as applicable. Due to early termination of enrolment, CSPv8 was never implemented and no new pts started treatment with AZD2811; all new patients transitioning into the maintenance phase were treated with durvalumab monotherapy. Further details will be provided in the SAP.

Baseline will be the last non-missing value obtained prior to the first dose/administration of study intervention in the induction phase, and any information taken after first dose/administration of study intervention in the induction phase is regarded as post-baseline information. All analyses will use this baseline unless otherwise specified.

An exploratory analysis using external control data will be conducted to compare AZD2811 + durvalumab to durvalumab from the CASPIAN study and will be reported outside of the CSR.

Induction Phase

The induction phase will be from the first dose of platinum-based induction therapy (cisplatin or carboplatin plus etoposide) + durvalumab until the first dose of AZD2811 + durvalumab in the maintenance phase.

Maintenance Phase

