Laboratory data for hematology and clinical chemistry will be summarized. The frequency of changes with respect to normal ranges between baseline and each post-treatment time point will be tabulated. Shifts from baseline to maximum value during treatment will be evaluated for urinalysis.

Vital Signs and Physical Examination

Vital sign parameters will be presented for each treatment group. Summary statistics for continuous variables cover number of participants, mean, standard deviation, minimum, quartile 1, median, quartile 3, and maximum. Frequency tables cover number and percentage of participants in the respective category.

The baseline value will be the latest result obtained prior to the start of study intervention in the induction phase.

For each scheduled post-baseline visit, descriptive statistics for all vital sign parameters will be presented for observed values and absolute change from baseline.

Changes in vital signs will be examined at each visit. Frequencies of clinically noteworthy values (defined in the SAP) occurring during the clinical study will be presented.

Details of vital sign analyses will be provided in the SAP.

All individual physical examination and targeted physical examination data will be listed only.

ECG

For the change from baseline summaries for ECG, the baseline value will be the latest result obtained prior to the start of study intervention in the induction phase.

The QTcF will be derived during creation of the reporting database using the reported ECG values (respiratory rate [RR] and QT):

$$\text{QTcF} = \text{QT}/\text{RR}^{(1/3)}, \text{ where RR is in seconds}$$

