3.1.2 Baseline measurements and change from baseline variables

Baseline will be the last non missing value obtained prior to the first administration of study intervention in induction phase and any information taken after first administration of study intervention will be regarded as post baseline information. All changes from baseline analyses use this definition of baseline regardless of the period being analyzed, e.g. no baseline for maintenance phase will be defined.

If two visits are equally eligible to assess subject status at baseline (e.g., screening or re-screening and baseline assessments both on the same date prior to first administration with no washout or other intervention in the screening period), the average should be taken as the baseline value. For non-numeric laboratory tests (i.e. some of the urinalysis parameters) where taking an average is not possible then the best value would be taken as baseline as this is the most conservative. In the scenario where there are two assessments on Day 1, one with time recorded and the other without time recorded, the one with time recorded would be selected as baseline. Where safety data are summarized over time, study day will be calculated in relation to date of first study intervention in induction phase. If no value exists before the first study intervention, then the baseline value will be treated as missing.

In all summaries change from baseline variables will be calculated as the post treatment value minus the value at baseline. For % change from baseline, calculate:

$$(\text{Post baseline value} - \text{Baseline value}) / \text{Baseline value} \times 100$$

Study day will be calculated as:

$$\text{Date of assessment} - \text{Date of first dose/administration of study intervention in induction phase} + 1$$

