3.2.3.4 Adverse Events

An adverse event (AE) is the development of any untoward medical occurrence in a subject or clinical study participant administered a medicinal product and which does not necessarily have a causal relationship with this treatment. The full definition of AEs and serious AEs (SAEs) can be found in the CSP Appendix B.

AEs and SAEs will be collected throughout the study, from date of informed consent until 90 days after the last dose of study intervention. Events will be defined as treatment emergent if they started after dosing or prior to dosing and worsen following study intervention. AEs which start in induction phase and subsequently worsen in maintenance phase will be defined as treatment emergent for both phases. AEs which start in induction phase and are ongoing, but not worsened, in maintenance phase, will be presented for induction phase only. For dosing days, AE start timing will be collected as well to identify pre- or post-dose AEs. AEs which start on Cycle 1 Day 1 but with start time before dosing are not considered treatment emergent. AEs which start/worsen on CCI [REDACTED] but with start time before dosing are considered as treatment emergent for induction phase only as long as they do not worsen in maintenance phase afterwards.

AEs with start or worsening date in safety follow-up period (within 90 days after the last dose of study intervention) will be presented along with AEs occurring in the phase from which the subject discontinued.

A flag will be created to indicate AEs which occur within the 90 days safety follow-up period but after initiation of the first subsequent therapy following discontinuation of study intervention.

The Medical Dictionary for Regulatory Activities (MedDRA) (using the latest or current MedDRA version) will be used to code the AEs. AEs will be graded according to the National Cancer Institute Common Terminology Criteria for AEs (CTCAE Version 5.0).

Maximum CTCAE grades on treatment overall and by phase will be derived.

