4.2.3.3 Laboratory

Clinical chemistry, coagulation and hematology results and change from baseline will be summarized using descriptive statistics (number of observations, mean, standard deviation, minimum, lower quartile, median, upper quartile and maximum) at each scheduled assessment time for continuous laboratory assessments). For a subset of laboratory variables (see Section 3.2.3.5) included in the current version of CTCAE, the CTCAE grade change from baseline to maximum on treatment will be summarized by phase. Urinalysis results will be listed only.

Number and percentages of clinically important changes will be presented by clinical chemistry, coagulation and hematology parameter.

Proportions of subjects with elevated liver test (elevated alanine aminotransferase (ALT) or aspartate aminotransferase (AST) (≥ 3 ULN), and elevated Total bilirubin ($\geq 2x$ ULN)) will be summarized and individual subject data for subjects with potential Hy's law will be provided.

Key subject information will be also provided for subjects with treatment-emergent clinical chemistry, coagulation or hematology values outside predefined criteria.

Plots for ALT and AST versus total bilirubin, expressed as multiples of upper limit of normal (ULN) and liver biochemistry test results over time will be created. The reference lines are 3x ULN for ALT, AST, and 2x ULN for Total bilirubin. In each plot, total bilirubin will be in the vertical axis.

Laboratory reference ranges as well as all individual laboratory data will be listed. Liver assessments, liver risk factors and liver signs and symptoms for all potential Hy's law cases will be listed separately.

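### Maintenance Phase change and shift displays are measured from the pre-induction value, so they combine induction carry-over with change on maintenance

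*SAP*

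**What the plan says.** **Baseline.** SAP 3.1.2 takes the last value before the first induction dose as baseline for all change analyses, "regardless of the period being analyzed, e.g. no baseline for maintenance phase will be defined". Protocol 9.4.1 sets the same default: "All analyses will use this baseline unless otherwise specified". Protocol 9.4.4 repeats it without an exception for vital signs ("The baseline value will be the latest result obtained prior to the start of study intervention in the induction phase") and for ECG ("For the change from baseline summaries for ECG, the baseline value will be the latest result" from before induction treatment).

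**Displays that use it.**
- SAP 4.2.3.3, laboratory: "the CTCAE grade change from baseline to maximum on treatment will be summarized by phase".
- SAP 4.2.3.5: QTcF and QTcB increases of more than 30 and more than 60 ms, also by phase.
- SAP 4.2.3.3 to 4.2.3.5: laboratory, vital-sign and ECG change from baseline over time. SAP 4.2 presents summaries by phase where applicable.

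**The value at the start of maintenance.** SAP 3.1.3 and 3.1.4 identify the assessment made before the first maintenance dose and assign it to induction. It is not used as a reference.

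**Adverse events.** SAP 3.2.3.4 separates the phases: "AEs which start in induction phase and are ongoing, but not worsened, in maintenance phase, will be presented for induction phase only".

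**The concern.** The design gives chemotherapy plus durvalumab and then adds a second marrow-toxic drug. Protocol Table 6 says of etoposide: "Dose-limiting bone marrow suppression is the most significant toxicity associated with etoposide therapy". It also says that anaemia on carboplatin may be cumulative. For AZD2811 the same table lists neutropenia as an identified risk and anaemia and thrombocytopenia as potential risks. The two phases can therefore move the same laboratory values, and a Maintenance Phase column measured from before induction adds the two movements together.

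The stake is how the safety tables are read. Under Protocol 9.4.2 and 9.4.4 efficacy is only listed (PK apart) and safety is reported in full. Protocol 4.1.2.2.1 describes two fatal neutropenic events that investigators attributed to AZD2811. Readers will look to the Maintenance Phase columns for what happened on AZD2811 plus durvalumab.

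**Working it through.** The plan states no figure on this point, so there is nothing to reproduce. The check is an identity, a look at the entry limits, and an illustration. All patient values, shifts and SDs below are assumptions.

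**1. Identity.** Let B be the pre-induction value, M the pre-dose value at the start of maintenance, and V a value on maintenance.

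Reported change V − B = (M − B) + (V − M) = induction carry-over + change on maintenance.

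The displayed change differs from the maintenance change by the whole of M − B.

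| Assumed case | B → M → V | SAP change (V − B) | Maintenance change (V − M) |
|---|---|---|---|
| Platelets, 10^9/L | 250 → 80 → 80 | −170 (−68%) | 0 |
| Haemoglobin, g/dL | 12.5 → 9.0 → 9.0 | −3.5 (−28%) | 0 |
| QTcF, ms | 405 → 440 → 440 | +35, counted as >30 | 0, not counted |
| ALT, × ULN | 4 → 1 → 4 | 0 | +3 |
| QTcF, ms | 440 → 400 → 445 | +5, not counted | +45, counted as >30 |

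The first three rows are carry-over shown as maintenance change. The last two are masking. Masking needs induction to have moved the value in the opposite direction. Protocol 5.1 makes this possible for ALT by allowing up to 5 × ULN at entry with hepatic metastases.

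**2. How far carry-over can reach in grade terms.** The documents do not print CTCAE cut-offs. I assume that Grade 2 starts below 1.5 for ANC and below 75 for platelets (both × 10^9/L), and spans 8 to <10 g/dL for haemoglobin.

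| Parameter | Induction entry (Protocol 5.1) | Start of a new cycle (Protocol 8.2.4) | Grade possible by carry-over alone |
|---|---|---|---|
| ANC | ≥1.5 | ≥1.5 | about Grade 1 at most |
| Platelets | ≥100 | ≥75 | about Grade 1 at most |
| Haemoglobin | ≥9.0 | no numerical limit | Grade 2 is conceivable |

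This takes the Protocol 8.2.4 rule to apply to Cycle 5. That section also requires other clinically relevant adverse effects to have resolved or returned to baseline, so a severe unresolved anaemia at Cycle 5 would sit badly with it. A haemoglobin of 9.0 still meets the study's own induction entry limit. Under the assumed cut-offs it would be tabulated as a maintenance shift to Grade 2 with no change on maintenance.

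**3. QTc increase rows.** The triplicate ECG shown in Table 1 is at screening. Protocol 8.2.3 calls for a recording before AZD2811 plus durvalumab and another about 15 minutes after the infusions. Under SAP 3.1.2 the post-dose value is compared with the recording from before all induction cycles.

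With a normal model, P(increase >30 ms) = 1 − Φ((30 − mean change)/SD). At SD 15 ms:
- Carry-over +20, maintenance effect 0. SAP baseline: 1 − Φ(10/15) = 25.2%. Maintenance baseline: 1 − Φ(30/15) = 2.3%. Expected count of 9: 2.27 against 0.20.
- Carry-over −20, maintenance effect +20. SAP baseline: 2.3%. Maintenance baseline: 25.2%. Expected count of 9: 0.20 against 2.27.
- Carry-over 0: the two baselines agree.

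For SD 10 to 20 ms, the first case runs from 15.9% against 0.1% to 30.9% against 6.7%. The second case is the mirror image.

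**4. Weight of one participant.** Protocol 9.4 gives 9 participants on AZD2811 plus durvalumab: 1/9 = 11.1 percentage points.

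**The case against.** **The baseline is deliberate and suits durvalumab.** It is stated consistently in both documents, and durvalumab starts in induction, so the pre-induction value is its natural reference. This stands. It is a reason to keep the present baseline alongside a second one, not a reason to have no display of change on maintenance.

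**Maintenance toxicity is not hidden.** A reader might infer that these tables conceal true maintenance toxicity, or that AZD2811 effects cannot be separated from chemotherapy at all. The documents do not support that:
- A renewed ALT of 4 × ULN would still appear in the liver plots, the out-of-range output and the listings. If graded against ULN, with Grade 2 above 3 × ULN (assumed), it also meets the by-phase rule for clinically important changes in SAP 3.2.3.5.
- The QTc rows above 450 and 480 ms are absolute.
- Observed values are summarised by visit and all individual values are listed.
- A Grade 2 or worse ANC or platelet value in maintenance must have arisen after entry, under the assumptions above.
- The durvalumab-monotherapy group carries a similar induction shift and gives a rough, non-randomised comparison.

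The cover is not complete. The assumed 400 → 445 ms case falls below the 450 ms row and shows only in observed values and listings.

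**AE and laboratory tables differ by design.** Protocol 8.3.5 makes a laboratory deterioration an AE only under certain conditions. So disagreement between the tables does not by itself prove an error. The contrast shows only that the SAP removes carry-over in one place and not in the other.

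**The protocol limits changes.** A reader might take the wording of Protocol 9.4.1 as enough authority for a new baseline. It is not enough for vital signs and ECG, which Protocol 9.4.4 fixes separately. That section also confines changes in the safety analyses to replacing summaries by listings.

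**Protocol 5.3.1 is weak evidence.** Its maintenance criteria came with version 8.0, which was not implemented. The ANC and platelet limits used above therefore rest on Protocol 8.2.4.

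**Conclusion.** The point holds in a limited form. Baseline-dependent Maintenance Phase displays show induction carry-over plus change on maintenance, and the carry-over includes induction durvalumab as well as chemotherapy. The result is clearest for haemoglobin, continuous change values and QTc. For ANC and platelet grade shifts it is limited to about Grade 1, given the assumed CTCAE cut-offs and the cycle-start rule applying at Cycle 5.

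Masking in the shift and change rows is possible, but nothing in the documents shows that it occurred. The documents also give no frequency for carry-over, so the QTc percentages are illustrations. The analysis is descriptive, so no test or decision rule is affected. What is affected is the reading of safety tables in which each AZD2811 participant counts for 11.1 percentage points. The value needed to show change on maintenance is already collected, so the addition is worth making.

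**What to change.** In SAP 3.1.2, define an additional maintenance baseline: the last non-missing value before the first maintenance dose. Use it for added Maintenance Phase displays of CTCAE grade shift, change from baseline (laboratory, vital signs, ECG) and QTcF/QTcB increases of more than 30 and more than 60 ms.

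Keep the pre-induction baseline for the Induction and Overall columns and for reading durvalumab effects. Add a footnote stating which baseline each column uses. Record the change in SAP Section 6, because Protocol 9.4.4 fixes the vital-sign and ECG baseline.

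Cost: one derived flag, a few extra table rows or columns, a footnote and a Section 6 entry. No new data are needed.

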3.1.3 Study periods

This study design consists of four study periods: screening, induction phase, maintenance phase and safety and survival follow-up.

Screening period

A subject enters the screening period at the date of completion of the informed consent. The screening period is scheduled to take up to 21 days (-21 Day to -1 Day). A subject may proceed into the induction phase if they meet all the eligibility criteria for the study otherwise they will be considered as a 'screen failure'. The screening period starts on the date of signed informed consent and ends either on date of screen failure or one day before first administration of study intervention.

Individuals who do not meet the criteria for participation in this study (screen failure) may be rescreened. Only one rescreening is allowed in the study. Participants must complete the rescreening within 4 weeks of the initial screen fail date (maximum of 7 weeks between initial consent and Cycle 1 Day 1 or second screen failure). Rescreened participants will receive the same participant number as for the initial screening.

Induction period

The induction phase starts when a subject receives the first administration of study intervention. The induction phase consists of **[REDACTED]** cycles. One cycle equals **[REDACTED]** of therapy given every **[REDACTED]**. In total, the planned duration of the induction phase is **[REDACTED]**. A subject is considered as having completed induction phase treatment, when all **[REDACTED]** cycles of treatment have been administered.

If a subject discontinues induction treatment prior to completing **[REDACTED]** cycles, the end date of the induction period is the day of end of induction treatment as per electronic case report form (eCRF) (as for eCRF completion guidelines (CCGs) this should be the date of last administration). The subject rolls over into safety follow-up period.

If a subject does not discontinue, does not withdraw consent, does not progress during the induction phase (tumor assessment at week 6 or with symptomatic PD) or does not die in the induction phase, subjects will be assessed for disease progression in week **[REDACTED]** which is used to confirm eligibility for maintenance therapy. Subjects who either progress or are not eligible for maintenance for other reasons will have the end date of induction phase at the date of the respective Response Evaluation Criteria in Solid Tumors (RECIST) v1.1 assessment. These subjects roll over into safety follow-up period.

Subjects who do not progress based on RECIST v1.1 or die, and are assessed to be eligible to continue into maintenance phase are considered to have the induction phase completed with end date one day before date of first study intervention in maintenance phase.

Maintenance period

Participants who have not progressed per RECIST v1.1 at the end of the induction phase and who meet maintenance phase eligibility criteria will continue into the maintenance phase of the trial and be treated with AZD2811 + durvalumab or durvalumab monotherapy as maintenance therapy. The maintenance phase starts when a subject receives the first administration of IP (AZD2811+durvalumab or durvalumab monotherapy) in the maintenance phase.

Assessments performed pre-dose on CCI [REDACTED] will be considered part of the induction phase unless based on the time collected indicates that the assessment occurred after the first dose in the maintenance phase. Assessments performed on day of dosing where time is not collected are assumed to have been done pre-dose. Maintenance phase end date is the date of end of last treatment during maintenance phase (maximum of end of treatment of AZD2811 and end of treatment of durvalumab). Subjects can discontinue from maintenance phase by withdrawal of consent, progression, death or if other discontinuation criteria are met. A subject who has been treated for a minimum of 2 years of maintenance treatment and continues to experience CR, PR, or SD, as demonstrated by radiographic measures, may be considered for treatment discontinuation.

Safety and survival follow-up period

Safety (concomitant medications and AEs/serious adverse events) will be followed up until 90 days after last dose. Start date of safety follow-up period is one day after end of treatment date in either induction or maintenance phase as per eCRF. The end date is

End date of Safety Follow-up = Date of last dose (regardless of phase) + 90.

Please note, for programming purpose the safety follow-up period duration might be derived as less than 90 days where date of last dose is not equal to date of end of treatment as per eCRF (if a subject discontinues between dose administrations).

For summary presentations, data during safety follow-up will be included in periods from which the subject rolled over to safety follow-up.

For subjects who were treated in maintenance phase, survival follow-up period starts one day after end of treatment date in maintenance phase as per eCRF. Data for overall survival, second progression and information for subsequent anticancer therapy will be collected, every 2 months +/- 1 week until DCO or their end of study.

